Resolving Psychological Stress

**University of San Francisco, California
San Francisco Veteran's Affairs Health Care System**

Principal Investigator: [name]

NCT03996876

Document Date: 9/11/2020

Study Protocol

Overview:

We will perform a phone screen or have participants fill out an online eligibility survey to determine eligibility for the study. Based on the answers to the screening questions, we will invite potentially eligible participants to attend an appointment at the San Francisco Veterans Affairs Medical Center to complete baseline assessments to include eligibility assessments and baseline testing. We may ask the questions from the eligibility screening in person if this is requested by the interested potential participant. The eligibility assessment will include the Clinician Administered PTSD Scale and the Structured Clinical Interview for the American Psychiatric Association's Diagnostic and Statistical Manual-V. For participants who are eligible after these assessments, we will complete baseline testing, which will include psychological and physiological tests. The eligibility and baseline assessments can take place over the course of one or two appointments. Following this, participants will be instructed on how to use the mobile app and how to complete the 15 days of training and assessments. Finally, after completing this program of training and assessments, they will return to the lab for follow-up assessments.

Inclusion Criteria:

To qualify for participation, participants will: 1) have current chronic PTSD (full- or sub-threshold) as defined by DSM-V criteria lasting at least 3 months and meeting at least one DSM-V criteria for threat sensitivity; 2) be aged 18-75; 3) have the ability to understand and comply with the training protocol and complete study assessments; 4) be either veterans or non-veterans; 5) have a DSM-V diagnosis of Alcohol Use Disorder.

Exclusion Criteria:

Exclusionary criteria include: 1) current ongoing trauma or trauma exposure within the past 3 months; 2) severe non-alcohol substance use disorder in the past 3 months (any level of alcohol use disorder is acceptable); 3) active suicidality; 4) lifetime history of schizophrenia or bipolar disorder I; 5) medical conditions including seizure disorders, neurological disorders, moderate or severe head injury (e.g., loss of consciousness greater than 30 minutes, severe traumatic brain injury), systemic illness affecting nervous system function, heart defect, or medically unstable injuries; 6) Recent change in psychotherapeutic treatment (e.g., psychotherapy, counseling) for PTSD or other psychiatric symptoms within the last 3 months, change in type of pharmacological treatment or a greater than 50% change in dose of pharmacological treatment within the last 3 months, or a planned change under one of these categories during the study period*; 7) subjects who, in the opinion of the investigator, are otherwise unsuitable for a study of this type. Individuals who are determined to require additional services, whether included or excluded from the study, will be referred to the VA or outside services if clinically appropriate. Additionally, individuals who report significant hearing difficulties but who are deemed eligible to participate in the study otherwise will be excluded from the fear-potentiated startle portion of the assessments at baseline and follow-up, as this task involves an acoustic startle.

15-Day Training and Assessment Phase:

The 15-day training and assessment phase will take place with the assistance of a mobile application called REPS (Resolving Psychological Stress). Eligible consenting participants will perform REPS training and assessments on the mobile application for 15 days. Participants will have up to three weeks to complete all the sessions. Participants will be instructed to complete a total of twelve days of training in conjunction with daily assessments of mood, stress, sleep and unusual events as well as three days of a more thorough assessment of mood, stress, depression, anxiety and PTSD symptoms once per week on the device. The training days involve approximately 15-minute long sessions of the REPS paradigm dot probe training and daily questions on the mobile app. Weekly assessment days should take 20 minutes on the mobile app. Participants may contact study personnel during office hours with questions or concerns via telephone or through email. We will contact participants by phone once per week to assess adherence to the protocol and to ensure that their device is functioning properly. We will assess adherence only by self-report. App-based follow-up assessments will take place at the end of 12 days of training. For participants who have not completed 12 days of training within 21 days of the start of training, we will push a follow-up assessment, which they will be asked to complete as soon as possible.

REPS Paradigm

Each training session with daily questions will last for approximately 15 minutes. At the beginning of the session, participants will be asked to report on their mood and emotions and stress exposure before beginning the REPS training session. During the training session, they will be exposed to threatening words in the ABM condition (e.g., death, crazy, worry) or neutral words in the control condition (e.g. hill, jersey, check). These are chosen based on their own ratings of 50 words. The ratings are entered into an algorithm which determines the most threatening words for that participant. On each trial, the participants will be exposed to a threatening (ABM) or neutral (control) word and a matched neutral word for a very brief period of time (500ms). The words will then disappear and one of them will be replaced by a probe in the form of either the letter E or F and the participant will be asked to indicate whether an E or an F appears. In the ABM training paradigm, the probe will replace the neutral stimulus all of the time, which is thought to train the participants to direct their attention towards a neutral stimulus in the context of a threatening stimulus. In the control condition, the probe will replace one set of neutral stimuli all of the time. There will be a brief inter-trial break (e.g., 500 - 1500 ms) between each trial. The participant will complete this training task for last approximately 10 minutes with an additional 5 minutes of daily questions.

Statistical Analysis Plan

Power analysis: This study is designed to yield estimates of effect size rather than to complete a definitive trial of ABM in PTSD.

Statistical Analyses: Descriptive analyses of behavioral and questionnaire data are used to assess feasibility and acceptability of REPS. Exploratory analyses examine the effects of intervention (attention bias modification versus control training) x time (baseline, follow up) on PCL-5 (PTSD Checklist-5) scores using mixed models. The PCL-5 was given via the mobile application immediately before participants starting their threat-related attention bias or neutral control attention training and at follow-up.

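### Does leaving unstated whether participants who do not finish training attend the lab follow-up undermine a planned result?

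*Combined protocol and SAP*

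**What the plan says.** The Overview sets out the study in order: screening, eligibility assessment, baseline testing, app training, lab return. Of baseline it says "we will complete baseline testing, which will include psychological and physiological tests". The next step opens with "Following this, participants will be instructed on how to use the mobile app", and the last is "Finally, after completing this program of training and assessments, they will return to the lab for follow-up assessments". No other sentence addresses who returns to the lab and when.

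The section on the 15-Day Training and Assessment Phase sets twelve training days plus "three days of a more thorough assessment of mood, stress, depression, anxiety and PTSD symptoms once per week on the device", with three weeks to finish. It foresees shortfall: "For participants who have not completed 12 days of training within 21 days of the start of training, we will push a follow-up assessment". That provision comes straight after the sentence on app-based follow-up and does not mention the lab.

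The Exclusion Criteria exclude people with significant hearing difficulties from the "fear-potentiated startle portion of the assessments at baseline and follow-up". No completion condition is attached there.

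Under Power analysis, the Statistical Analysis Plan says "This study is designed to yield estimates of effect size rather than to complete a definitive trial of ABM in PTSD". Under Statistical Analyses it plans descriptive work on feasibility and acceptability, and an exploratory model of the "effects of intervention (attention bias modification versus control training) x time (baseline, follow up) on PCL-5 (PTSD Checklist-5) scores using mixed models". It states that the PCL-5 is collected through the app.

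**The concern.** Taken at its word, the Overview makes finishing the program a condition of the lab visit. The authors saw that some participants would fall short and wrote a follow-up rule for the app, but no matching rule for the lab. Lab follow-up data would then come from completers alone.

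Completion occurs after assignment to attention bias modification or control training. A by-arm comparison among completers is no longer a comparison of everyone who started. It is biased if completion rates differ between arms, or if completers and non-completers differ by more in one arm than in the other. The weekly app questionnaires could partly stand in for missing lab symptom scores. They could not do so for startle, which is nowhere described as measured on the app. In a study meant to produce effect-size estimates, this looks like a weakness that one sentence of protocol text could remove.

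**Working it through.** The plan gives no figure to reproduce: no arm size, completion rate, dropout allowance or lab effect size. The check has two parts.

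**1. What the text supports**

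| Place | On the lab follow-up | On non-completers |
|---|---|---|
| Overview | Last step, after the program | Silent |
| Exclusion Criteria | Startle at baseline and follow-up; hearing restriction only | No completion condition |
| 15-Day Training and Assessment Phase | Silent | Follow-up pushed after day 21, apparently on the app |
| Statistical Analysis Plan | No lab outcome named | PCL-5 on the app, so covered by the pushed follow-up |

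No text gives non-completers a lab visit and none denies one. The only between-arm analysis does not use lab data.

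**2. How large the bias could be if an unplanned lab contrast were made in completers only**

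Every input here is an assumption. Let p be the proportion completing in an arm and d the completer minus non-completer difference in mean change, in SD units. The mean among all starters is the completer mean minus (1 − p)d, so

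bias = (1 − p_ABM) × d_ABM − (1 − p_Ctl) × d_Ctl.

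*Same gap in both arms, d = 0.3 to 0.5:*
- Equal completion: 0.
- 70% versus 80%: (0.3 − 0.2) × 0.3 = 0.03; × 0.5 = 0.05 SD.
- 60% versus 80%: (0.4 − 0.2) × 0.3 = 0.06; × 0.5 = 0.10 SD.

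The sign depends on which arm completes less.

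For 60% versus 80%, with n starters per arm and SD of change 1, the standard error is SE = √(1/(0.6n) + 1/(0.8n)). With k = bias/SE, coverage of a 95% interval is Φ(1.96 − k) − Φ(−1.96 − k).

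| n per arm | SE | k | Coverage |
|---|---|---|---|
| 20 | 0.382 | 0.16-0.26 | 94.7-94.2% |
| 50 | 0.242 | 0.25-0.41 | 94.3-93.0% |
| 100 | 0.171 | 0.35-0.59 | 93.6-91.0% |

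*Different gap by arm, equal completion of 70%, d = 0.5 in one arm and 0 in the other:* bias = 0.3 × 0.5 = 0.15 SD, and SE = √(2/(0.7n)).

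| n per arm | SE | k | Coverage |
|---|---|---|---|
| 20 | 0.378 | 0.40 | about 93% |
| 50 | 0.239 | 0.63 | about 90% |
| 100 | 0.169 | 0.89 | about 86% |

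*What inviting everyone would gain.* Suppose half of non-completers attend (r = 0.5), with attendance unrelated to outcome. The arm term becomes [(1 − p) − (1 − p)r/(p + (1 − p)r)] × d.
- p = 0.6: 0.4 − 0.2/0.8 = 0.150.
- p = 0.8: 0.2 − 0.1/0.9 = 0.089.
- Difference 0.061d, so the residual bias is 0.018-0.031 SD.
- Bias removed: (0.200 − 0.061)d = 0.04-0.07 SD, or 0.11-0.18 standard errors at 20 per arm.
- Attendance becomes 80% and 90%, and the standard error falls by about 10% (√(2.361/2.917) = 0.90).
- Extra visits: 0.5 × (0.4 + 0.2) × n = 0.3n, that is 6, 15 or 30 for 20, 50 or 100 per arm.

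**The case for a change.** The best argument for acting is that the omission is real, that the authors dealt with the same problem for the app, and that startle data missed at the lab cannot be recovered elsewhere. Equal completion rates are no safeguard: the different-gap case gives 0.15 SD, and at 100 starters per arm coverage falls to about 86%. The remedy would be one sentence using the existing 21-day limit.

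The omission stands, and so does the principle that a completers-only contrast is not a contrast of all starters. Three things weaken the case for a change.

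- The literal reading is not the only one. The sentence ends a chronological account, the startle text carries no completion condition, and the training section keeps following people who fall short instead of dropping them.
- The contrast at risk is not planned. The Statistical Analysis Plan's effect-size aim is tied to no lab measure; its only by-arm model is on the PCL-5.
- The gain is uncertain. It assumes that non-completers who travel to the lab are typical of all non-completers, although people who stop a 15-minute app task but still attend may be selected. The documents also give no reason to expect completion to differ: both arms do the same probe task for the same time, and differ in word content and so in what the probe replaces.

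**Conclusion.** No change to the plan follows. The documents leave a detail unstated, but following them as written makes no planned result wrong: the feasibility and acceptability summaries are descriptive, and the exploratory PCL-5 model draws on app data with a route for non-completers.

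Any harm is confined to a by-arm lab estimate that the Statistical Analysis Plan does not name. Under the assumed inputs its bias would be 0 to 0.15 SD, below one standard error in every case worked at 20 to 100 starters per arm. These are illustrations, not bounds, since the documents give neither sample size nor completion rates.

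The gap is one that analysts fill sensibly. Anyone reporting startle by arm would ordinarily show how many attended the lab in each arm and by completion status, and would call the estimate completers-only if non-completers were not seen. The past-tense account of PCL-5 collection suggests that data collection may already be over, in which case new invitation wording could achieve nothing. If it is not over, the choice is between some extra lab visits and a small, uncertain gain on an unplanned comparison, and leaving the text alone is a fair trade-off.

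### Adherence is to be assessed by self-report alone and no other measure is stated, although all 15 scheduled days take place in the app

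*Combined protocol and SAP*

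**What the plan says.** The relevant text is in the protocol section on the 15-day training and assessment phase. It describes a weekly call: "We will contact participants by phone once per week to assess adherence to the protocol and to ensure that their device is functioning properly". The next sentence reads: "We will assess adherence only by self-report".

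The same section puts the whole programme in the app: "Eligible consenting participants will perform REPS training and assessments on the mobile application for 15 days". On the 12 training days, "The training days involve approximately 15-minute long sessions of the REPS paradigm dot probe training and daily questions on the mobile app". On the 3 assessment days, "Weekly assessment days should take 20 minutes on the mobile app". Participants have three weeks to finish, and one rule depends on how many training days were done: "For participants who have not completed 12 days of training within 21 days of the start of training, we will push a follow-up assessment". The source of that count is not given.

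Under REPS Paradigm, the session opens with questions: "participants will be asked to report on their mood and emotions and stress exposure before beginning the REPS training session". The task follows, and on each trial "the participant will be asked to indicate whether an E or an F appears".

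The SAP, under Statistical Analyses, says that feasibility and acceptability will be described from behavioural and questionnaire data, and that the PCL-5 was collected through the app. It does not define adherence or name a completion variable.

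**The concern.** Feasibility is a stated purpose of the analysis. For an intervention delivered by app, the number of scheduled sessions that participants completed is one of the most basic descriptive results. The protocol names self-report as the sole means of assessing adherence, although every scheduled activity calls for input on the study device. A record made when the session is done is a more direct measure than an answer given on the phone up to a week later.

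What is at stake is the meaning of any adherence figure in the feasibility description. As the plan stands, a reader could not tell whether such a figure was recorded or recalled, what its denominator was, or whether an abandoned session counted as done.

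**Working it through.** No sample size, power or error rate enters this point. The check is a count of the schedule, followed by a comparison of the passages.

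**1. Reproduce the plan's own figure.** The 15-day section gives 12 training days and 3 weekly assessment days: 12 + 3 = 15, which matches the stated length of the phase.

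**2. How much of the schedule is in the app?** Training days and assessment days are both placed on the app or device, so 15 of 15 days. Using the approximate durations in the 15-day section and REPS Paradigm:

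- dot probe task: 12 × 10 = 120 minutes
- daily questions: 12 × 5 = 60 minutes
- weekly assessments: 3 × 20 = 60 minutes
- total: 120 + 60 + 60 = 240 minutes (check: 12 × 15 + 3 × 20 = 240)

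No scheduled activity in this phase takes place away from the device.

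**3. Does each activity need a response?** Yes. The questions and weekly assessments are answered in the app, and each dot probe trial asks for an E or F. The task is therefore not passive exposure.

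**4. What would count as a completed training day?** The mood and stress questions come before the task. A day with question entries only shows at most about 5 of the 15 minutes and none of the roughly 10-minute task. Equally, a single E/F response shows that the task was begun, not that it was done. The documents give no number of trials per session, so a trial-count threshold cannot be set from them. Reaching the end of the session is a criterion that needs no such number.

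**5. Why two counts?** Assessment days are 3/15 = 20% of the schedule, so a count of training days alone would leave them out. One day is 1/12 = 8.3 percentage points of a participant's training adherence, or 1/3 = 33.3 points of assessment adherence. These figures show how coarse the two scales are. They do not estimate error.

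**6. Which window?** Three weeks are allowed for all sessions (3 × 7 = 21 days), and the rule for the pushed follow-up assessment uses 21 days from the start of training. A definition of adherence should use the same window.

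**7. Is another adherence measure stated anywhere?** No. The 21-day rule implies that someone or something counts training days, but its source is unnamed. The SAP's behavioural data could include session counts, but it does not say so.

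**The case against.** The strongest reply is that the sentence explains only how staff ask about adherence on the weekly call, which the preceding sentence introduces. On that reading the SAP's behavioural data, most naturally the task responses, may already supply session counts, and the 21-day rule suggests that a completion count exists. The fault would then be one of wording. This reading is plausible and cannot be excluded. It does not remove the gap, because no passage says that app records are used for adherence, and the one sentence that addresses the source says self-report only.

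Three further objections stand and limit the point. Retention of session-level data is inferred from the in-app responses, the app-delivered PCL-5 and the 21-day rule; it is not stated. The plan names no adherence endpoint or threshold and no analysis that depends on adherence. The study is also meant to estimate effect sizes and is not a definitive trial.

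Some stronger conclusions are tempting but unsupported:

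- A reader might infer that reported adherence will be overstated. The documents give no misreporting rate and no direction.
- A reader might infer that the follow-up assessment will be pushed to the wrong participants. The source of the count is unstated, which does not show that it is wrong.
- A reader might infer that the treatment comparison is compromised. The intervention-by-time model for PCL-5 does not use adherence.

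**Conclusion.** The point holds as a cheap improvement. Taken literally, the protocol chooses recall as its only adherence measure for a programme carried out wholly in an app. On the narrower reading, it states no adherence measure beyond the call. Either way the text should name the measure and define a completed session.

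The consequence is confined to the descriptive feasibility result. Its numerical size cannot be derived from the documents, and the PCL-5 analysis as specified is unchanged. The recommendation to use app records assumes that session-level data are retained. If they are not, what remains is to describe the adherence result accurately.

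**What to change.** Replace the self-report sentence in the 15-day section with:

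> Adherence is the number of training days (of 12) on which the dot probe task was recorded in the app as completed to the end of the session, and the number of weekly assessment days (of 3) recorded as completed, both within 21 days of the start of training. Partly completed sessions are reported separately. Self-report at the weekly call is supplementary.

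In the SAP, under Statistical Analyses, add that these app-recorded counts are summarised by arm in the descriptive feasibility analysis. State also that the same count of training days is used for the 12-day/21-day follow-up assessment.

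If session-level app data are not retained, say so and label the result as self-reported adherence.

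The cost is a few sentences and a small extra tabulation, with no added visits or participant burden. Device faults could cause sessions to be under-counted, which is why the weekly call stays as a supplement. The adherence figure may also turn out less favourable. Because this is a reporting definition, it can still be applied after data collection, provided the records exist.

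### Does the neutral-word control leave the ABM contrast unable to show what it is meant to show?

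*Combined protocol and SAP*

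**What the plan says.** The REPS Paradigm section describes both conditions. On the stimuli, participants are told apart by word type: "they will be exposed to threatening words in the ABM condition (e.g., death, crazy, worry) or neutral words in the control condition". The threat words are tailored to the person: "The ratings are entered into an algorithm which determines the most threatening words for that participant". Each trial then shows a pair: "On each trial, the participants will be exposed to a threatening (ABM) or neutral (control) word and a matched neutral word".

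On the probe, the ABM rule is "In the ABM training paradigm, the probe will replace the neutral stimulus all of the time", and the control rule is "In the control condition, the probe will replace one set of neutral stimuli all of the time". The same section gives the rationale for ABM in hedged terms, as a procedure "which is thought to train the participants to direct their attention towards a neutral stimulus in the context of a threatening stimulus".

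The 15-Day Training and Assessment Phase section sets the dose: "Participants will be instructed to complete a total of twelve days of training".

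The Statistical Analysis Plan says the study is meant to produce effect-size estimates and is not a definitive trial. It uses descriptive analyses for feasibility and acceptability, and labels as exploratory a mixed model of PCL-5 with intervention, time and their interaction. It names the two arms and says nothing about which component of ABM is responsible for any difference.

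**The concern.** The rationale for ABM rests on the contingency: the probe sits behind the neutral word while a threat word competes for attention. A reader who takes that as the hypothesis under test would expect a control that shows the same threat words without the contingency. The control here does the reverse. It keeps a fixed contingency and removes the threat words.

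A PCL-5 difference could then come from training attention away from threat, from repeated viewing of one's own most threatening words, or from both. Viewing those words need not be inert in people with PTSD who must meet at least one threat-sensitivity criterion to enter. A null result could in principle be two effects that cancel. The words are also visible to participants, who complete the PCL-5 themselves on the app.

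An effect size is a stated product of the study. If it were carried forward as the effect of attention retraining alone, it would be mislabelled.

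**Working it through.** The SAP gives no figure on this point to reproduce. The check has three parts.

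**1. What differs between the arms in training (REPS Paradigm)**

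| Feature | ABM | Control |
|---|---|---|
| Word pair | threat + matched neutral | neutral + matched neutral |
| Probe location | neutral word, 100% | one neutral set, 100% |
| Threat words on screen | yes | no |
| Attention steered away from threat | yes | no |

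Task, session length, app and predictability of the probe are matched. The last two rows differ together.

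**2. Can the two features be separated?**

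Code each arm as (intercept, threat-word exposure, away-from-threat contingency).

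- ABM = (1, 1, 1) and control = (1, 0, 0). The rank is 2 for 3 parameters. The difference is (0, 1, 1), so the contrast estimates exposure plus contingency and neither alone.
- With a control showing the same threat-neutral pairs and the probe equally often behind each word, control = (1, 1, 0). The difference is (0, 0, 1), which is the contingency alone.
- With all three arms the rank is 3 of 3, and both components are estimable.

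The aliasing is therefore real. Neither the mixed model nor a larger sample removes it.

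**3. How unequal is the exposure?**

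Inputs from the document: words shown for 0.5 s, an inter-trial break of 0.5 to 1.5 s, about 10 minutes (600 s) of training per session, 12 training days. Response time is not given and is assumed.

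Trial length = display + response + break; trials per session = 600 / trial length; total = 12 × trials per session.

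| Assumed response | Break | Trial length | Trials per session | Total over 12 |
|---|---|---|---|---|
| 0.6 s | 1.5 s | 2.6 s | 600/2.6 = 231 | 2,769 |
| 0.6 s | 0.5 s | 1.6 s | 600/1.6 = 375 | 4,500 |
| 1.0 s | 1.5 s | 3.0 s | 200 | 2,400 |
| 0.5 s | 0.5 s | 1.5 s | 400 | 4,800 |

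Control training gives 0. Two limits apply. The totals assume all 12 sessions are done, whereas the protocol provides for people who do not finish within 21 days. And the zero holds for training trials only: words are chosen from participants' ratings of 50 words, and the text does not confine that rating to the ABM arm. A single rating would not come close to matching the training exposure.

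These figures count presentations. They do not measure bias in PCL-5, and the document contains nothing that would convert one into the other.

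**The case for a change.** The strongest case for a change is that an effect size is what the study sets out to deliver, so what it measures should be stated, and one sentence in the SAP would do it. The protocol's rationale points to the contingency, the comparator does not isolate it, and no reason is given for choosing neutral-word training. A deliberate choice still deserves a stated estimand. A control with threat words and a balanced probe would also equalise the visible word content.

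Part of this stands. The two components cannot be separated, and a report that credited attention retraining alone would go beyond the data.

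The rest does not carry a change to the plan:

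- The SAP makes no mechanistic claim. The only mechanistic sentence is in the description of the task, and it is hedged.
- Steering attention away from threat requires threat to be present. Threat words are part of ABM as the protocol defines it, so an ABM-versus-control effect is already the effect of the package. The comparator is openly described as neutral. A sentence saying so largely restates the paradigm text and changes no model, dataset or estimate.
- The balanced-probe control has its own cost: it may be active training, and it could then shrink the estimated effect of delivering ABM. It answers a question about a component, whereas the present control answers one about the package. Nothing in the document says the aim is to isolate a component, and experienced statisticians could defend either choice.
- Cancelling effects and harm or benefit from exposure are possibilities without a supporting figure. What participants know of the other arm is not shown in the text available, and both arms perform the same letter-identification task.

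**Conclusion.** The observation is correct, but it does not call for a change. The exploratory interaction on PCL-5 estimates ABM as delivered (personalised threat words plus the contingency) against neutral-word attention training. It cannot isolate attention retraining, and the SAP does not say that it does. As a package comparison it is valid.

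The imbalance in exposure is about 2,800 to 4,500 presentations against none in control training at an assumed 600 ms response, or 2,400 to 4,800 across 0.5 to 1.0 s, with full completion of twelve sessions. The conclusion does not depend on those assumptions, since any non-zero count gives the same aliasing.

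The stakes are modest: the analysis is exploratory, the study is not definitive, and an effect size taken into a later trial of the same package against the same control would be the right input. The choice of comparator is a fair trade-off. The SAP also describes PCL-5 collection in the past tense, so replacing the control may no longer have been possible. Authors may, as good reporting practice, say that the effect size is that of the package and not of attention retraining alone; the plan can stand without it.
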